Different methodologies have been used to try and increase uptake of contraceptives in the postpartum setting. One study looked at the provision of contraceptives in the home, and found that clients had less days not covered by effective contraceptive use during the 90 days following a first birth [5]. The authors suggested that home dispensing of hormonal contraceptives may improve women's postpartum contraceptive use and should be explored as an intervention in communities where contraceptives are not easily accessible [5]. This study design did not include offering LARC in the home.

A research group from the Department of Obstetrics and Gynecology at the University of Colorado wanted to observe the actual clinical impact that such LARC devices might have on repeat pregnancy and contraceptive continuation rates among adolescents [3]. They conducted a prospective observational study of immediate postpartum implant insertion and found a 2.6% pregnancy rate one year post-placement, compared to an 18.6% pregnancy rate among the control group [3]. Their research shows that high continuation rates of postpartum LARC can translate into reduced immediate postpartum pregnancy rates. Downstream benefits of using LARC in this population also appeared to include a 2-percentage point decrease in preterm birth, which was an unexpected but highly beneficial outcome [3].

This study combines the two prior aforementioned study in a new population; it desires to look at home-based provision of contraceptive care, including LARC in the form of the progesterone-only implant called Jadelle®, and observing how this reduction of a barrier to access increasing uptake of all contraceptives, including abstinence. The hypotheses are:

Hypothesis 1: Offering routinely available contraceptives in a home setting can increase incidence of contraceptive initiation in a postpartum rural Guatemalan population.

Hypothesis 2: Increased use of long-acting reversible contraceptives placed in the home setting in a rural, postpartum Guatemalan population will decrease short-interval pregnancy rates.

Research Objectives: This study has the following objectives:

Objective 1: Increase uptake of routinely offered contraceptives in the postpartum setting by providing them to women at their home-based postpartum visit.

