Objective 2: Determine short-interval pregnancy, satisfaction, and continuation rates among women who received contraceptives in the home versus those that sought postpartum contraceptives through routine care.

Objective 3: Determine short-interval pregnancy, satisfaction, and continuation rates among women who opted for long-acting versus short-acting reversible contraceptives that were provided in the home setting.

Objective 4: Document side effects and adverse events occurring in the study population.

Methodology:

Study Design: This study is a cluster randomized trial of an intervention to increase uptake of postpartum contraception by providing them to women in their home and observe the effect on uptake in the community of interest. We have eight communities involved the healthcare services provides by the CHD that will be combined into six clusters, for study purposes. The clusters are independent of one another, except that some nurses offering the contraceptives may cover more than one cluster. Patients may also move between clusters over the course of the trial. Women will be recruited for enrollment into the CHD, and subsequently the study, blind to whether their cluster will be offered home-based contraception in the postpartum setting.

Operational Definitions/Proposed Intervention: This is a prospective community cluster-randomized study of a home-based intervention to increase uptake of postpartum contraceptives and study the direct effect on short-interval pregnancy, continuation, and satisfaction rates. The study has two phases.

Phase 1: The first phase fulfills AIM 1 and will involve a cluster randomized trial of the intervention, which is to bring and offer Jadelle[®], among all other routine postpartum contraceptive options, to the women in their homes, compared to routine care. Currently, around 4% of the population opts for Jadelle[®], which is less than expected, likely due to the fact that previously, Jadelle[®] was only offered

at a clinic inconvenient to the study population that required significant time and travel costs. Recently, implant availability has increased in the region due to the work of a non-governmental organization, and the nurses within the CHD were trained on implant placement. Therefore, Jadelle®, which was previously offered as part of the standard of care but not routinely available, now is accessible.

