Visit 1: At the postpartum visit in their home, patients will be enrolled in the study and provide informed consent. Once they have agreed to participate in the study, they will be offered postpartum contraception in the home in the intervention group, and through routine care (at CHD pharmacy or clinic location) in the control group. The nurses will bring all routinely available medications to the patient's home for those in the intervention clusters, including pills, condoms, Jadelle®, and depot medroxyprogesterone acetate. Patients who are breastfeeding will not be offered estrogen-containing methods. Participants in both the intervention group and control group will also be offered IUD placement; regardless of group, they will need to present to an area clinic setting for placement should they choose this method. Women opting for Jadelle® will receive immediate implant placement, and women that opt for other methods will receive their method of choice. 99% of patients in the community service program are seen for this postpartum visit, which is part of the standard of care for patients in this region.

Ninos Sanos Visits: The follow-up visits will occur through routine care as part of the Ninos Sanos program, into which all patients in the Madres Sanas program are automatically enrolled. Mothers are seen with their infants monthly in their home, including visits at six and twelve months after delivery. At these routine visits, the mothers enrolled in the study, in both groups, will complete a survey. The surveys will assess patient continuation rates and satisfaction with the contraceptive method of choice. Patients will also be queried about side effects such as: irregular bleeding, weight gain, headaches, rash, chest pain, moodiness, insertion site pain, cramps, acne, nausea, hair loss, or issues with breastfeeding after device placement. All patients will be questioned regarding repeat

pregnancy at these visits, as well, including outcomes of repeat pregnancies such as delivery, termination of pregnancy, or spontaneous abortion. We anticipate that this survey will take about 10 – 20 mins to administer. Additionally, the study nurses will perform a survey of their comfort and satisfaction with administering contraception in the home, which will be performed after enrollment is complete. These questionnaires are included with the submission.

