continuation, satisfaction, and pregnancy rates. They will have the option to leave the study at any point without any repercussions for their clinical care. We will have these questionnaires performed in a private location, in a one-on-one setting to increase comfort with discussing these issues, and patients will also be able to complete the questionnaire privately if they are literate and do not need assistance.

The primary foreseeable risk of all parts of the study is a breach of privacy and/or confidentiality. Study data will be stored securely in REDCap, which is HIPAA compliant and controls access on a study-by-study basis through the use of unique usernames and passwords. REDCap allows data fields to be flagged as identifiers, and investigators will utilize this feature to remove identifiers from datasets, which are exported for analysis.

Utilization of postpartum contraceptives, including placement of the implant how contraceptive use affects short interval pregnancy rates are the specific aims of this study; the study cannot be performed without offering contraceptives, including device placement. Fortunately, these medications are already in use in the study population and are non-experimental methods. Therefore, with proper counseling and informed consent, we believe the risks of the procedure will be acceptable to the patients and their partners.

Analysis Plan:

Methods & Models: The primary outcome of this study is contraceptive uptake rates in the intervention group. This study, with 200 women enrolled (100 from intervention clusters and 100 from control clusters) will be powered to detect a change in Jadelle uptake rates from 3% to 15% at 85% power and 5% significance, with an intra class correlation of 2%.

The satisfaction surveys will be administered at the six and twelve month well-child visits and will primarily assess patient experience with the medications, including side effects, continuation rates, and pregnancy rates. This quantitative analysis will provide direct feedback in terms of real-world use of contraceptives, their success rates, and their acceptability to the patients, which will also provide baseline research for future interventions to address issues surrounding patient choice of and satisfaction with different method of contraception, including the implant.

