Programs Used: The analysis plan for this will use summary statistics to describe the patient population as well as the outcomes. We will use Student t (normally distributed variables) or non-parametric medians (non-normally distributed variables) tests for continuous data and χ^2 or Fisher's exact tests (for variables with cell sizes <5) for categorical data. Bivariate analyses will be performed to compare the groups. Variables that are significant ($P < 0.05$) in the bivariate analyses will be included in a logistic regression to determine independent predictors of repeat pregnancy. SPSS statistical software (version 24.0.0; IBM SPSS Inc, Chicago, IL) will be used for all the analyses.

References:

2. Guttmacher Institute. Sexual and reproductive health of young women in Guatemala. Online 2014, accessed 1/17/17 (<https://www.guttmacher.org/sites/default/files/factsheet/fb-dd-guatemala.pdf>)
4. LARCs: IUD and Implant Options. Planned Parenthood. Accessed 1/23/17 (<https://www.plannedparenthood.org/planned-parenthood-mar-monte/patient-resources/long-acting-reversible-contraception/larc>)

Timeline: After we have obtained IRAC/COMIRB APPROVAL and Francisco Marroquin University Ethics approval to proceed with the study, we will begin the study. We anticipate the first step of the trial to start January 2018. We expect this to be a 24-month study; the timeline will appear as follows:

Months	Activities
Dec 2017	Training, Jadelle placement refresher course

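### The plan does not commit to comparing short-interval pregnancy by assigned cluster in all enrolled women, and its listed tests ignore the six clusters

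*Combined protocol and SAP*

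**What the plan says.** The title and the Operational Definitions/Proposed Intervention section present the trial as measuring an effect of a cluster-randomised home intervention on short-interval pregnancy. Under Research Objectives, Objective 2 states the comparison for pregnancy, satisfaction and continuation as "women who received contraceptives in the home versus those that sought postpartum contraceptives through routine care". It is the only home-versus-routine pregnancy comparison that the document spells out. Objective 3 compares women by the type of method they chose.

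Visit 1 describes the randomised contrast as an offer of contraception "in the home in the intervention group, and through routine care (at CHD pharmacy or clinic location) in the control group". Under Ninos Sanos Visits, surveys are given in both groups and "All patients will be questioned regarding repeat" pregnancy. Study Design allows women to move between clusters and does not say how they are then counted.

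The Analysis Plan states that "The primary outcome of this study is contraceptive uptake rates in the intervention group". Under Programs Used it lists t, non-parametric, chi-square and Fisher tests, says that "Bivariate analyses will be performed to compare the groups", and adds a logistic regression for predictors of repeat pregnancy, entered on bivariate P < 0.05. It names no analysis population, no as-assigned rule and no adjustment for clusters.

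**The concern.** What was randomised is the offer, by cluster. Receiving or seeking a method happens after randomisation and is what the intervention is meant to change. A comparison restricted to women who received or sought contraception therefore sets two selected groups side by side and removes much of the path from the offer to fewer pregnancies. Women with no method, who would be expected to have the highest pregnancy rate and to be fewer in the intervention arm, drop out.

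Two analysts could follow this plan faithfully and report different pregnancy results: one by arm in all women, the other by receipt. The one who works by arm would still be led to tests that treat 200 women in six clusters as independent, which overstates the evidence.

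**Working it through.** **The plan's own figure.** The document gives no power or precision for pregnancy. Its one calculation is for implant uptake, 3% against 15%, 100 women per arm. With mean proportion 0.09, the null standard error is √(2 × 0.09 × 0.91/100) = 0.0405 and the alternative standard error is 0.0396. Then Φ[(0.12 - 1.96 × 0.0405)/0.0396] = 0.848, as printed. It reproduces only with no allowance for the stated intraclass correlation.

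**Step 1. Literal reading against all enrolled women.**

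Inputs from the document:
- implant use 3% (control) and 15% (intervention), from the power statement;
- 2.6% pregnant at one year with an implant and 18.6% in the comparison group, from the cohort cited in Background.

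Assumed inputs:
- any-method uptake 50% against 70%;
- 5% to 15% pregnant among users of other methods;
- 18.6% to 30% pregnant with no method, the lower end borrowed from the cited cohort.

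Formulas, with u = uptake, j = implant use, o = rate in other users and q = rate with no method:
- users only: [j × 0.026 + (u - j) × o]/u
- all women: j × 0.026 + (u - j) × o + (1 - u) × q

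*Smallest loss (o = 15%, q = 18.6%)*
- Control: 0.03 × 0.026 + 0.47 × 0.15 = 0.0713. Users 0.0713/0.5 = 14.3%; all 0.0713 + 0.5 × 0.186 = 16.4%.
- Intervention: 0.15 × 0.026 + 0.55 × 0.15 = 0.0864. Users 0.0864/0.7 = 12.3%; all 0.0864 + 0.3 × 0.186 = 14.2%.
- Difference: all women -2.2 points, users only -1.9.

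*Largest loss (o = 5%, q = 30%)*
- Control: 0.03 × 0.026 + 0.47 × 0.05 = 0.0243. Users 4.9%; all 0.0243 + 0.15 = 17.4%.
- Intervention: 0.15 × 0.026 + 0.55 × 0.05 = 0.0314. Users 4.5%; all 0.0314 + 0.09 = 12.1%.
- Difference: all women -5.3 points, users only -0.4.

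| Other users | No method | All women | Users only |
|---|---|---|---|
| 15% | 18.6% | -2.2 | -1.9 |
| 10% | 18.6% | -2.6 | -1.1 |
| 10% | 30% | -4.9 | -1.1 |
| 5% | 30% | -5.3 | -0.4 |

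At this uptake the users-only comparison drops 50 + 30 = 80 of 200 women. Background speaks of "increasing uptake of all contraceptives, including abstinence". If abstinence counts as a method and uptake is 80% against 90% (assumed), 20 + 10 = 30 women are dropped, and the same two corner cases give -1.8 against -1.6 and -2.8 against -0.3 points.

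**Step 2. By-arm reading with the listed tests.** Six clusters of about 33.3 women and an intraclass correlation of 0.02 give a design effect of 1 + (33.3 - 1) × 0.02 = 1.65. With no true difference, a chi-square test that ignores clusters rejects with probability P(|Z| > 1.96/√1.65) = P(|Z| > 1.53) = 0.127. A simulation (200,000 trials, beta-binomial, clusters of 34, 33 and 33 per arm, 17% pregnant in both arms) gives about 0.13 for chi-square and 0.049 for a t test on the six cluster proportions.

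**Step 3. Precision and power when clusters are respected.** Applying 2.6% and 18.6% at the planned implant uptake gives 0.03 × 0.026 + 0.97 × 0.186 = 18.1% and 0.15 × 0.026 + 0.85 × 0.186 = 16.2%. The standard error without clustering is √[(0.1812 × 0.8188 + 0.1620 × 0.8380)/100] = 0.0533. The 95% half-widths are:
- clustering ignored: 1.96 × 0.0533 = 10.4 points;
- with the design effect: 10.4 × √1.65 = 13.4 points;
- with t on 4 degrees of freedom: 2.776 × 0.0533 × √1.65 = 19.0 points.

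Power of the 4-degree-of-freedom test (noncentral t) is about 9% for 19.8% against 14.9% (the third row of the table) and about 21% for 18.6% against 9.3% (an assumed halving).

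**The case against.** The best defence is that Objective 2 simply names the arms. Visit 1 describes them in nearly the same words, the protocol uses the word group for the arms, the three outcomes in Objective 2 match those listed for the cluster-randomised intervention, and pregnancy is asked of everyone. Satisfaction and continuation presuppose a method, which may explain the wording. This is quite plausible. A reader might infer that the authors have chosen an as-treated analysis; the document does not show that. What stands is that nothing commits to the by-arm comparison in all women, and that the by-arm reading still leads to unclustered tests.

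The size in step 1 is mostly assumption, and the loss can be as small as about 0.3 points. The users-only calculation also only approximates the text, since the control side literally includes women who sought a method without obtaining it. Both limits are accepted.

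Three further inferences go beyond the documents:
- That the P < 0.05 screen will exaggerate the intervention effect. This would need arm to be screened and its effect reported only from the regression. The stated purpose of that model is to find predictors, and nothing says the intervention effect comes from it.
- That intervention-arm IUD users would be counted as routine care. Visit 1 does say "regardless of group, they will need to present to an area clinic setting for placement should they choose this method", but no rule assigns them to the other side and no IUD uptake is given.
- That Hypothesis 2 promises an effect by arm. It says that greater use of long-acting methods "will decrease short-interval pregnancy rates", which is a question about use. The arm-level promise comes from the title and the Operational Definitions/Proposed Intervention section.

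**Conclusion.** The point holds as an uncommitted comparison together with an unsuitable test, and should be corrected. It does not show that a post-randomisation comparison has been chosen.

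Followed literally, Objective 2 can hide anything from almost none to nearly all of a pregnancy effect, depending on rates that the document does not give. On the by-arm reading, the nominal 5% error becomes about 13%. That figure rests on the protocol's own 2% correlation, equal clusters and an assumed 17% pregnancy rate.

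The consequence is confined to the pregnancy conclusions. Uptake is the primary outcome, and its definition does not depend on this wording.

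**What to change.** Reword Objective 2 and the Programs Used paragraph along these lines: *Short-interval pregnancy will be compared between all women enrolled in intervention clusters and all women enrolled in control clusters, by cluster allocation at enrolment, including women who took no method or who later move.*

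In addition:
- use a method that respects the clusters, for example a t test on the six cluster proportions (4 degrees of freedom), and report the difference with its 95% interval;
- state that the groups compared are the randomised arms;
- label Objective 3, and any comparison by receipt or among users only, as non-randomised;
- keep the logistic regression as an exploratory predictors model and do not take the intervention effect from it.

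The change needs no new data, and the t test is available in SPSS. The price is precision: a half-width of about 19 points instead of about 10 with clustering ignored, and power of roughly 9% to 21% in the cases above. The trial is unlikely to show a pregnancy effect, so the report should rest on the interval and not on the P value.

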Based on previously collected data, we expect that during our study timeframe around 260 women will meet eligibility criteria over the course of one year. The clusters will be randomly assigned by a biostatistician. This study, with 200 women enrolled (100 from intervention clusters and 100 from control clusters) will be powered to detect a change in Jadelle uptake rates from 3% to 15% at 85% power and 5% significance, with an intra class correlation of 2%.

[figure not shown]
Group	Proportion Positive	N Per Group	Standard Error	95% Lower	95% Upper
Population 1	0.03	100			
Population 2	0.15	100			
Rate Difference	-0.12	200	0.04	-0.20	-0.04

Alpha= 0.050, Tails= 2, Power = 0.848

Power computation: Normal approximation (unweighted mean p)
Precision computation: Log method

Phase II: Phase two of the study are six month and one-year follow-up visits that occur as part of routine care. Patients are immediately enrolled on delivery into Ninos Sanos, the early childhood health and development program offered through the CHD. Women and infants are seen monthly as part of the program, including routine visits at six and twelve months. At these sessions, mothers will be subject to a questionnaire regarding their contraceptive satisfaction and continuation habits, as well as whether or not they became pregnant since their delivery. This frequent and routine contact will ensure that patients are easily located for performing the follow-up questionnaire, but also will have no problem contacting study personnel if they have issues with their contraception or to report adverse events. We will also hold a focus group (interviews and surveys) for providers regarding their comfort and satisfaction with provision of care in the home setting before the study begins and after enrollment is complete.

Study Flow Diagram:

Study Visits: Patients who participate in the Community Health Services program through the CHD receive routine antepartum counseling on postpartum contraception in their home. At this visit, which is part of routine care, all women receive an educational intervention on contraception, which includes Jadelle® and the risks/side effects, benefits, and alternatives to the immediate postpartum implant.

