Jan – Dec 2018	Study Execution: Intervention in 3 study clusters, routine care in 3 study clusters
January 2019	Data analysis
Jan – Dec 2019	Follow-up Questionnaires: all participants
January 2020	Data analysis

Budget:

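### Eight communities are merged into six clusters, 3 v 3, with no reason given; the stated 85% power ignores clustering, and randomising all eight would probably, but not certainly, recover some power

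*Combined protocol and SAP*

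**What the plan says.** Under Methodology, Study Design, the protocol reports eight communities served by the programme "that will be combined into six clusters, for study purposes". No reason follows. The same paragraph describes the clusters as independent, except that a nurse may serve more than one, and adds that patients may move between them during the trial. The Timeline fixes the allocation: "Intervention in 3 study clusters, routine care in 3 study clusters".

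The sample-size paragraph under Phase 1, repeated under Analysis Plan, Methods & Models, plans for "200 women enrolled (100 from intervention clusters and 100 from control clusters" and claims to "detect a change in Jadelle uptake rates from 3% to 15" per cent "at 85% power and 5% significance, with an intra class correlation of 2" per cent. The printed output beneath the Phase 1 paragraph reads "Alpha= 0.050, Tails= 2, Power = 0.848" and gives the method as a normal approximation for two proportions.

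Programmes Used lists t tests or non-parametric tests, chi-square or Fisher tests, and a logistic regression for repeat pregnancy. It names no cluster-level test, no randomisation test and no adjustment for clustering. Community sizes are not given anywhere.

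**The concern.** In a cluster trial the number of randomised units sets the degrees of freedom and, for a fixed number of women, the mean cluster size and so the design effect. With equal sizes, merging eight units into six cuts the degrees of freedom from 6 to 4 and raises the mean size from 25 to 33.3. At these small numbers the t critical value changes a good deal, from 2.447 to 2.776.

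Power for Jadelle uptake may therefore be lost with no stated benefit in return. The reader cannot see this loss, because the 85% claim does not reflect the number of clusters. Once the clusters have been allocated, the choice cannot be undone.

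**Working it through.** **Inputs from the protocol.** Eight communities, six clusters (Study Design); 3 v 3 (Timeline); 100 women per arm, 3% v 15%, ICC 0.02, two-sided alpha 0.05, printed power 0.848 (Phase 1).

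**Assumptions made here.** Equal cluster sizes in steps 2 and 3; illustrative unequal sizes in step 4; a cluster-level t test, which the plan does not name.

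**1. Reproduce the stated figure.** With n = 100 per arm and mean proportion 0.09:
- SE under the null = √(2 × 0.09 × 0.91 / 100) = 0.0405
- SE under the alternative = √((0.03 × 0.97 + 0.15 × 0.85) / 100) = 0.0396
- Power = Φ((0.12 − 1.96 × 0.0405) / 0.0396) = 0.848

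This matches the printed value with no design effect. Neither the ICC nor the number of clusters enters it.

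**2. Add the ICC, equal sizes.** Design effect = 1 + (m − 1) × 0.02; effective n = 100 / design effect. The t-test power uses the noncentral t with noncentrality 0.12 / SE, where SE = 0.0396 × √(design effect).

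| | Six clusters | Eight clusters |
|---|---|---|
| Mean size m | 33.3 | 25 |
| Design effect | 1.647 | 1.48 |
| Effective n per arm | 60.7 | 67.6 |
| Power, normal critical values | 64.0% | 68.7% |
| Degrees of freedom | 4 | 6 |
| Noncentrality | 2.363 | 2.493 |
| Power, cluster-level t test | 43.8% | 55.1% |
| 95% CI half-width (points) | 2.776 × 5.08 = 14.1 | 2.447 × 4.81 = 11.8 |

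The gain is 4.7 points with normal critical values and 11.4 with the t test. A beta-binomial simulation of the t test (40,000 trials) gives about 45% and 57%, a gain of about 12. Over other ICC values the t-test gain is 8.8 points (ICC 0), 10.8 (0.01), 11.2 (0.03), 10.2 (0.05) and 7.6 (0.10).

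**3. Randomisation test.** With 3 v 3 there are C(6,3) = 20 allocations, so the smallest two-sided P is 2/20 = 0.10. With 4 v 4 there are C(8,4) = 70, so it is 2/70 = 0.029.

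**4. Unequal communities.** Put the ICC of 0.02 at community level, and let the merger pool the two smallest communities in each arm.

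*Weighted by size.* The variance of the arm mean is the same before and after merging, with design effect 1 + 0.02 × (Σs²/100 − 1), where s is the community size within an arm. Only the degrees of freedom change:
- 33/33/17/17: design effect 1.531; 46.3% (six) v 53.8% (eight)
- 40/40/10/10: design effect 1.660; 43.5% v 50.6%
- 42/42/8/8: design effect 1.711; 42.5% v 49.4%

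The gain is about 7 points, within a range of 6 to 8.

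*Unweighted t test on cluster proportions (simulated).*
- 33/33/17/17: 48% (six) v 54% (eight)
- 40/40/10/10: about 44% v 44%, no gain
- 42/42/8/8: 43 to 44% v 39%, a loss

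**The case against.** The strongest case is that merging may be sensible and merely unexplained. If some communities are very small, pooling them steadies the cluster proportions, and step 4 shows that an unweighted analysis may then gain nothing from eight units. Shared nurses and movement of patients are both routes for contamination, and more borders between arms could widen them. As an illustration with an assumed figure: if 11% of control women took up Jadelle at the intervention rate, control uptake would rise to 0.03 + 0.11 × 0.12 = 4.3%, enough to cancel the whole 11-point gain. All of this stands. It makes the benefit conditional and calls for a stated reason. It does not show that the merger solves either problem, since the protocol expects shared nurses and movement between the merged clusters too.

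Three stronger readings are tempting, and the documents do not support them.
- *A 3 v 3 trial cannot reach P < 0.05.* That limit applies to a randomisation test, which the plan does not name. A cluster-level t test can reach 5% with six clusters, and so can the planned chi-square test, although that test ignores clustering. Nor is 4 v 4 a strong rescue: simulated power of its randomisation test is only about 34%.
- *Eight clusters add 11 points.* That holds for a t test with equal sizes, and the sizes are unknown.
- *The merger costs power and saves nothing.* Nurse coverage by community is not described, so this cannot be judged.

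**Conclusion.** The point holds in conditional form. The merger is unexplained, it leaves 4 degrees of freedom, and a randomisation test on 3 v 3 could not go below 0.10; that is a limit of the design, not of the planned analysis. The firmest finding is that 85% is not the power of this design at its own ICC: it is about 64% by normal approximation or 44% by a cluster-level t test.

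Eight clusters would give about 69% or 55% with equal sizes. Across the cases examined, the change runs from a loss of about 5 points (unweighted t test, very unequal sizes) to a gain of about 12 (t test, equal sizes). The result rests on an ICC of 0.02, the 3% v 15% rates and assumed community sizes. The loss is worth avoiding where feasible, but it does not invalidate the trial. Leaving the ICC out of the power figure is the larger fault, and eight clusters do not cure it.

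**What to change.** - **Study Design and Timeline.** Before allocation, randomise the eight communities four per arm with the same 200 women. If very small communities, shared nurses or movement between communities make this unworkable, keep six and state that reason in Study Design.
- **Programmes Used.** Specify an analysis based on the actual number of clusters, weighted by cluster size if sizes differ.
- **Phase 1 and Methods & Models.** Replace the 85% with power that includes the design effect and cluster-level degrees of freedom, and report the community sizes on which it rests.

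The protocol is dated 30 August 2017 and enrolment is planned from January 2018, so the cost is revised wording and an allocation draw on eight units, with no more women to enrol. The downsides are possibly more contamination between neighbouring communities in different arms, less equal cluster sizes, and a stated power well below 85% under either layout.
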